- *Minimizing risks to confidentiality & privacy.* Recognizing that loss of privacy is a serious issue, we have put strong methods in place to protect identifiable data. First, all investigators and research personnel will receive training on protection of human subjects. Second, identifiable information will only be made available to a few specific research personnel who will need access to the data purely for study purposes. All paper records will be stored in secure locked cabinets only accessible to study personnel. Third, the mHealth application will be developed with security as top priority. The security features include storage of data in an encrypted format within a password-protected smartphone, secure https-based data transmission between the mHealth application and the server based at VUMC, robust user-level authentication to access data, and automatic log out after a period of inactivity. Other features that minimize risk to confidentiality and privacy by utilizing neutral signifiers on the application, that would not be readily linked to HIV status (for example using the text “it’s time” or another chosen text to pop up on the phone screen when it is time to take an ART dose, not including any symbols or logos readily linked to HIV, and not using the name of the clinic or of antiretroviral medications on the application screen). The choice of text and formatting will be informed by user-centered design. Fourth, patients will provide specific consent for the provision of phone or home-based outreach if the mHealth app signals non-adherence for 5 days or more. This is a practice that patients at NIMR are accustomed to, as phone and/or home-based outreach was standard for patients who defaulted from care before cutbacks in clinic funding. Concerted efforts will be made to minimize the use of any paraphernalia (labeled vehicles, clothing on clinic staff) that might identify participants as HIV patients, and no communication will be initiated in the presence of individuals who are not authorized by the patient to be present. Nonetheless, this risk will be explicitly discussed with participants at the time of enrollment and consent for study participation. Fifth, youth will be counseled on the low risk of data breach with these safeguards, but also on how to further minimize data breach when phones are shared. These safeguards will be present in the demonstration session introducing the participants to the application, and additional steps may be taken to prioritize safety and privacy, as guided by the focus group discussions. Sixth, we will work with the IRBs at Vanderbilt and NIMR to apply for a certificate of confidentiality, to ensure that the information collected through the mHealth application remains secure by preventing the academic institutions conducting the research from disclosing data collected in the course of the study to outside organizations or agencies. This will be an important step to mitigate the potential risk of abuse of data for unforeseen or unanticipated use. Finally, only NIMR staff will have access to data in the electronic health record. Requested clinical data will be shared with the study team and linked to patients in the pilot cohort (Aim 2) using a unique identifier. Identifiable data will be removed and not shared where feasible and also will be removed from servers as soon as is consistent with completing project tasks.

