3. STUDY OBJECTIVE AND HYPOTHESIS

SPECIFIC AIM: To establish the feasibility, acceptability, and preliminary efficacy of *PEERNaija*, an mHealth intervention designed to harness peer influence as an incentive to promote medication adherence among a pilot cohort of 50 AYA living with HIV in Nigeria.

[figure not shown]
Hypothesis: *PEERNaija* will be feasible, acceptable, and show preliminary efficacy in improving ART adherence.

4. METHODS (TO INCLUDE STUDY DESIGN, DETERMINATION OF SAMPLE SIZE, EXCLUSION/INCLUSION CRITERIA, ANALYSES OF DATA, ETC.)

Eligibility and Enrollment: We will conduct a prospective pilot study of the *PEERNaija* application for 50 AYA living with HIV in Nigeria. Patients will be recruited from the APIN HIV clinic and will be eligible for this study if they 1) own a smartphone (on which they are willing to download *PEERNaija*), 2) are 14-29 years of age, 3) are on ART, and 4) demonstrate the ability read simple text language in English. Patients will provide written informed consent for study participation.

Intervention Description: All participants will receive daily medication reminders, access to the virtual support group, and other key features identified in Aim 1. In addition, participants will be randomized to receive the social incentive (n=25) or the social plus financial incentive (n=25), *PEER+* and be followed for 24 weeks.

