For the **social incentive**, the application will track the participant's individual adherence score (% of doses taken), track the top scorers (leaderboard), and provide a figure highlighting the proportion of their peers with poor (<80%), medium (80-94%), or high (>94%) adherence scores. The display of the individual's adherence score relative to peer scores is considered a descriptive norm and is meant to portray "what most people are doing," as young people often inaccurately estimate behaviors for their peer groups. Participants will also receive an injunctive norm, or an indication of what they ought to be doing. This will come in the form of an emoji or congratulatory vs. motivating text for those with high or low adherence scores, respectively. When coupled with descriptive norms, injunctive norms have counteracted regression to the mean for individuals who demonstrate desirable behaviors relative to their peers.²⁸ For the **financial incentive**, the top 5 scorers in the *PEER+* arm will be eligible win a lottery prize each month of the 24 week pilot of 1000 NGN of "data" that can be directly loaded onto the winner's phone [Figure 1]. Behavioral economics theory tells us that individuals are more averse to losses than rewarded by gains, so that even incentives/prizes should be framed in terms of losses.⁴⁰ Accordingly, participants in the financial incentive arm will receive weekly motivating messages such as "take your dose today or you lose the chance of winning the lottery." Potential language for these messages will be informed by user-centered feedback in Aim 1.

Patients will be seen in clinic at enrollment, 6 weeks, 12 weeks, and 24 weeks. At enrollment, patients will complete a comprehensive survey assessing demographics and mobile phone usage patterns. We will also collect data on a range of factors known to impact medication adherence including, depression (WHO SQ-20 scale), self-efficacy (medication taking self-efficacy scale), stigma (Berger's HIV stigma scale), symptoms (HIV symptom severity scale), and social support (SPS-10 scale).⁵⁵⁻⁵⁸ Adherence will be assessed using from the application itself (percentage of doses completed) and from 3 validated measures: 1) self-reported visual analog scale (VAS), 2) medication possession ration (MPR), and 3) AIDS Clinical Trials Group (ACTG)

adherence questionnaire.⁵⁹⁻⁶¹ Baseline CD4 count and HIV RNA will be obtained from the clinic record (within 3 months of enrollment).

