Study Outcomes: The outcomes of interest for this study are feasibility, acceptability, adoption, and preliminary efficacy, and will be measured at 24 weeks. Preliminary efficacy will be assessed by comparing change in HIV viral load, and adherence from baseline to 12 weeks, and baseline to 24 weeks. We hypothesize that the *PEERNaija* mHealth application will be feasible and acceptable, and show preliminary efficacy in improving HIV virologic control. The study outcomes will be assessed through a combination of a) questionnaires administered to study participants b) clinical measures or correlates of adherence measured at baseline and at each study visit, and (c) analysis of usage data collected during routine use of the application. Chat feature use will be measured by monitoring the monthly frequency of posts per participant in addition to the thematic content.

Data analysis: Study feasibility and acceptability will be measured by analyzing the content of the feedback surveys at each study visit, and the FGDs at study end. Adoption will be assessed by analyzing usage data. Preliminary efficacy will be assessed by conducting a pre–post comparison of adherence measures, HIV viral load, and adoption measures at baseline, 12, and at 24 weeks in the two study groups (*PEER* and *PEER+*). De-identified chatroom the chat posts will be downloaded from the coordinator application, and reviewed from weeks 0-12 and 12-24.

5. ETHICAL CONSIDERATION. CONSENT DOCUMENTATION (TRANSLATION TO LOCAL LANGUAGES WHERE APPLICABLE) AND PATIENT INFORMATION LEAFLET (WHERE APPLICABLE)

A. Risks to the Subjects

A.1. Human Subjects Involvement and Characteristics. This study will involve several participants, namely:

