- **Patients** (Aims 1 & 2) Adolescents and young adults (AYA) aged 14-29 years will be recruited from the APIN-managed HIV clinic at the Nigerian Institute for Medical Research. Patients are legally emancipated for HIV care at the age of 15 in Nigeria and can provide consent for clinical care and research participation. For the pilot proposed in Aims 2, Patients will be eligible for this study if they 1) own a smart phone (on which they are willing to download *PEERNaija 2*) are 14-29 years of age, 3) on ART, 4) demonstrate the ability read simple text language in English “*My phone will remind me to take my drugs*”, and 5) have a documented history of poor adherence defined as history of virologic failure in the preceding 3 months, medication possession ratio (MPR) <80%, or referral to clinic counselor for adherence counseling).
- **Providers** (Aim 1) Providers eligible to participate in this study include physicians, nurses, and counselors whose primary responsibility is for the care of patients living with HIV, and who have focused responsibility for AYA. They will be recruited from the NIMR HIV clinic.
- **Other key stakeholders** (Aim 1) Important stakeholders who will also participate in this study include parents (of AYA living with HIV), HIV program leaders from NIMR and representatives from the primary public health organization focused on HIV outcomes in the country, Nigeria’s National Agency for the Control of AIDS (NACA).

A.2. Sources of material. Data will be obtained through several modalities. A set of data will be obtained through focus group discussions and study questionnaires. We will also collect and use several forms of electronic data, including: (a) data collected as part of routine patient care that is contained within NIMR’s electronic health record system, (b) data entered by patients as part of their use of the mHealth application, and (c) logging, activity and location utilized by the mHealth application.

A.3. Potential risks. Overall, potential risks associated with participation in the study are unlikely and of low risk.

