6. STATISTICAL ANALYSIS PLAN (SAP)

Primary Outcomes

Primary outcomes are feasibility, acceptability, and appropriateness of the PEERNaija app. These will be assessed through Weiner’s validated feasibility of intervention measure (FIM), acceptability of intervention measure (AIM), and appropriateness of intervention measure (IAM) at six months. The FIM, AIM, and IAM surveys each contain four statements and participants are asked to rate their level of agreement to each statement on a Likert scale of 1-5, with 1 being “completely disagree” and 5 being “completely agree.”

Participants will answer study team-generated questions assessing the acceptability and appropriateness of individual app features and the app overall via feedback questionnaires administered at 12 and 24 weeks.

Secondary Outcomes

Secondary outcome is preliminary efficacy on viral load. This will be assessed by comparing change in HIV viral load (from baseline to 24 weeks), and self-reported adherence from baseline to 12 weeks, and baseline to 24 weeks. ART adherence will also be assessed at baseline and six months using a visual analogue scale where participants indicated the percentage of prescribed ART doses taken over the past 30 days.

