Comparisons of primary outcomes (feasibility, acceptability and appropriateness) will be performed by comparing mean FIM, AIM, and IAM scores respectively between PEERNaija and PEERNaija+ at 24 weeks using two-sample t-tests. These constructs will additionally be addressed by comparing questions from feedback questionnaires, specifically assessing percentage of reminders received and whether or not reminders or chat messaged were intrusive, whether it was helpful to see their peers' adherence scores, whether they would use the app after the study, and whether they would recommend the app to a peer.

Comparisons between secondary outcomes (viral load and self-reported adherence) will be assessed by conducting a pre-post comparison of adherence measures at baseline, 12, and at 24 weeks, and pre-post comparison of viral load measures at baseline and 24 weeks in the two study groups (*PEERNaija* and *PEERNaija+*), using paired tests (e.g., paired t-tests, signed rank tests, or McNemar's tests, as appropriate), with a significance level set at $p \leq .05$ (2-tailed test). Further, self-reported preliminary efficacy will be assessed via response to feedback questionnaire question asking whether the app helped them to miss fewer medication doses and responses across study groups using Chi-square tests.

To further explore associations between outcomes and variables of interest, univariate regression analyses will be performed. Linear regression will be applied to continuous outcomes, including the primary outcomes (FIM, AIM, and IAM score) and self-reported adherence; while logistic regression will be used for binary outcomes such as viral suppression status at the study end.

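### The two eligibility lists conflict; if the one requiring poor adherence applies, a qualifying viral load can also be the baseline, and the within-arm paired tests can show a fall through regression to the mean

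*Combined protocol and SAP*

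**What the plan says.** **Eligibility.** Section 4 (Eligibility and Enrollment) gives four criteria: smartphone ownership, age, and "3) are on ART, and 4) demonstrate the ability read simple text language in English". Section 5.A.1, for the same pilot, repeats these and adds a fifth. Patients must "have a documented history of poor adherence defined as history of virologic failure in the preceding 3 months, medication possession ratio (MPR) <80" per cent, or have been referred to the clinic counsellor for adherence counselling. These three routes are alternatives.

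**Baseline.** Section 4 states: "Baseline CD4 count and HIV RNA will be obtained from the clinic record (within 3 months of enrollment". No enrolment draw for HIV RNA is described. Study Outcomes, in the same section, speaks in general terms of "clinical measures or correlates of adherence measured at baseline and at each study visit".

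**Arms.** There are 25 participants per arm. "All participants will receive daily medication reminders, access to the virtual support group, and other key features identified in Aim 1"; the arms differ only in the added financial incentive.

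**Analysis.** The SAP says "Secondary outcome is preliminary efficacy on viral load". It plans a "pre-post comparison of viral load measures at baseline and 24 weeks in the two study groups", "using paired tests (e.g., paired t-tests, signed rank tests, or" McNemar's tests), at two-sided 0.05. It names no between-arm test of viral load. The only other viral-load analysis is an exploratory univariate logistic regression of suppression at study end, with no predictors named.

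**The concern.** The 3-month window for qualifying failure and the 3-month window for baseline HIV RNA can be filled by the same laboratory result. Patients chosen because one value was high tend to be lower when next measured, even if nothing has changed. A paired test within an arm cannot tell that fall from benefit. Because both arms are exposed to it and no between-arm test of viral load is planned, no planned comparison of change removes it.

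Viral load is the named secondary efficacy outcome, section 4 hypothesises better virologic control, and section 7 presents the project as the basis for a larger trial. A significant fall within an arm could therefore be carried forward as evidence for the app when it came from how patients were selected.

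**Working it through.** The documents give no power calculation, SD or expected viral-load change, so there is no figure of the plan's to reproduce.

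**Inputs from the documents.** n = 25 per arm; paired tests at two-sided 0.05, so nominally 2.5% in the direction of improvement (exact McNemar is conservative and runs lower); 40% failing. The 40% is section 2's retrospective figure for youth in care one year after starting ART, not a stated expectation for this pilot.

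**Assumed, not in the documents.** The number k of 25 who enter by failure with that value as baseline; the correlation ρ between baseline and 24 weeks (0.6–0.9); no app effect. The other 25 − k are taken either as all non-failing or as unselected on viral load.

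**Expected shift.** Take log10 viral load as standard normal with the failure cut at the 60th percentile, z = 0.253, where the density is 0.386. Mean above the cut = 0.386/0.4 = 0.966. Mean below = −0.386/0.6 = −0.644. Then

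expected change = −(1 − ρ) × [k × 0.966 + (25 − k) × m]/25 SD,

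with m = −0.644 (others non-failing) or 0 (others unselected).

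- k = 25: −0.39 SD at ρ = 0.6 and −0.10 SD at ρ = 0.9.
- k = 13, ρ = 0.6: −0.4 × (12.56 − 7.73)/25 = −0.08 SD with others non-failing; −0.4 × 12.56/25 = −0.20 SD with others unselected.
- k = 8, ρ = 0.6, others non-failing: −0.4 × (7.73 − 10.95)/25 = +0.05 SD. The arm then holds fewer failing patients than the assumed clinic, and the shift reverses.

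**Chance of a significant false improvement.** The paired-t figures are simulated (40,000 runs per cell). The exact McNemar figures assume re-suppression q = 20–40% and rebound q × 0.4/0.6, which holds failure prevalence at 40%.

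| Entering by failure (of 25) | Others | Paired t | McNemar |
|---|---|---|---|
| 25 | – | 18–61% | 38–97% |
| 18 | non-failing | 8–19% | 5.5–26% |
| 18 | unselected | 11–33% | 14–58% |
| 13 | non-failing | 4–5% | 0.6–2.2% |
| 13 | unselected | 8–19% | 6–27% |
| 8 | non-failing | 1–2% | under 0.1% |
| 8 | unselected | 5–10% | 2–9% |

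One McNemar cell can be checked by hand. With all 25 failing at baseline there are no rebounds, and significance needs at least 6 re-suppressions (2 × 0.5^6 = 0.031; 5 give 0.063). P(Binomial(25, 0.2) ≥ 6) = 0.38.

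With no selection (k = 0, others unselected) the paired t-test gives 2.5%. The signed-rank test, with the lowest 40–50% of clinic values set to a detection floor, gives 15–53%, 8–33% and 4–20% for k = 25, 18 and 13.

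**Alternatives.**

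- A separate baseline taken after the qualifying value gives 2.3–2.7% if all pairs of values are equally correlated. If correlation decays with time it gives 16–51% at k = 25.
- A between-arm comparison adjusted for baseline rejects in 4.6–5.6% of runs, two-sided, in every case run.
- The 95% CI half-width for that comparison is t(2n − 3) × √(1 − ρ²) × √(2/n). With n = 25 it is 2.012 × 0.8 × 0.283 = 0.46 SD at ρ = 0.6 and 2.012 × 0.436 × 0.283 = 0.25 SD at ρ = 0.9. With 20 completers per arm it is 0.51 and 0.28 SD. These ignore values at the detection floor.

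**The case against.** The strongest reply is that the size is undetermined. Failure is one of three routes; the share using it, the correlation and the pilot's failure rate are all assumed, and the results run from below nominal to very large. That stands: the documents do not show where the pilot would fall.

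It can also be said that the stakes are modest. Viral load is secondary and labelled preliminary, the primary comparisons of the feasibility, acceptability and appropriateness scores (FIM, AIM, IAM) are between arms and untouched, and no viral-load go/no-go rule is stated. That too stands, but the SAP sets a significance threshold for these tests and the project is meant to lead to a larger trial.

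A third reply is that a between-arm comparison does not test the app, since both arms have it. This is correct, and it limits what the pilot can claim. It does not make the within-arm test sound.

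A reader might take the general wording in Study Outcomes to mean a fresh baseline measurement. The sentence on HIV RNA is the specific one, and it names the clinic record.

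**Conclusion.** The concern holds conditionally. The eligibility conflict is plain on the page. If the section 5.A.1 list applies, nothing bars the qualifying viral load from serving as baseline, and the planned paired tests can then show a fall with no app effect. The inflation is serious if most entrants qualify by failure and small or absent if few do. At about half failing it is essentially absent only if the other entrants are all non-failing; if they are unselected, the false-improvement rate is 8–19% (paired t) or 6–27% (McNemar). All of this rests on the assumed 40% failure rate, the correlation or re-suppression range, and no app effect.

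A reader might infer that the viral-load tests are biased as they stand, or that any significant fall would be an artefact. The documents do not support that. Under the section 4 list failing patients may enter, but not because of that value, and this selection does not arise. Nor does the problem reach the primary outcomes. The end-of-study suppression regression uses no change score and is not exposed to it, although it is neither baseline-adjusted nor specified as an arm comparison. This should be settled before viral load is analysed; it does not undermine the pilot's main purpose.

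**What to change.** 1. Reconcile the eligibility lists in sections 4 and 5.A.1; this review does not choose between them. Align Study Outcomes with the section 4 sentence on where baseline HIV RNA comes from.
2. Whichever list is kept, add to the SAP a comparison of log10 HIV RNA at 24 weeks between the randomised arms, adjusted for baseline log10 HIV RNA. State that it estimates only the added financial incentive and is imprecise.
3. Only if the poor-adherence criterion stands: make that comparison the inferential viral-load analysis; record each patient's qualifying route at enrolment; state whether the qualifying value may serve as baseline; report within-arm change as a descriptive estimate with 95% CI, by route where numbers allow; and do not attribute it to the app.

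If the section 4 list is kept, the planned within-arm tests stay as they are, alongside item 2.

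Replacing the baseline with a later clinic-record value for those patients who have one is not advised. It would define baseline differently between patients and may not remove the bias.

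The cost is SAP wording, one eligibility correction and, only under section 5.A.1, one enrolment-form field. Item 2 uses data already collected. The real price, under section 5.A.1, is that the pilot cannot claim a tested virologic effect of the app itself, and estimates by route will rest on small groups.

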2. RATIONALE/ JUSTIFICATION OF STUDY (CITING RELEVANT CRITERIA)

Preliminary work in Nigeria from [name] (co-PI) Care4Life program demonstrated, in one retrospective analysis, that 40% of AYA who remained in care one year after starting ART had virologic failure (HIV RNA >1000 copies/mL).¹² In a multisite study of adherence as measured by medication possession ratio (MPR; proportion of prescribed doses of ART picked up from the pharmacy), AYA with MPR >94% had a marked reduction in the risk of virologic failure in the first year on ART compared to those with MPR <80% (aRR 0.43, p<0.001).⁵³ Nonetheless, 26% of AYA with optimal adherence by MPR (>94%) still had virologic failure, highlighting discordance between ART pick-up from the pharmacy and ART taking behaviour among some youth.⁵⁴ **These data underscore need for adherence support measures that help AYA to take their medicines, not just get them from the pharmacy.** To gain a better understanding of smart phone ownership and use in the proposed study setting, 20 AYA attending an adolescent HIV clinic in Lagos, Nigeria were surveyed; **95% owned a mobile phone (84% with smart phones)** and most were frequent users of SMS/text messaging, instant messaging services, and social media platforms. Thus, our proposed mHealth intervention, which leverages an existing mHealth application focused on improving medication taking for youth with HIV, is well suited to support the adherence needs of AYA in this setting.

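### The paired viral load analysis drops anyone without a clinic-record HIV RNA within 3 months of enrolment, no eligibility rule requires one, and the loss may be selective

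*Combined protocol and SAP*

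**What the plan says.** On the baseline value, the assessments paragraph of section 4 (Methods) states: "Baseline CD4 count and HIV RNA will be obtained from the clinic record (within 3 months of enrollment". It gives no study draw and no fallback when the record is empty.

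There are two eligibility lists. The one in section 4 asks for a smartphone and then "2) are 14-29 years of age, 3) are on ART, and 4) demonstrate the ability read simple text language in English"; nothing in it concerns viral load. The one in section 5, A.1 adds a fifth criterion, documented poor adherence, met by any of three alternatives: "history of virologic failure in the preceding 3 months, medication possession ratio (MPR) <80%, or referral to clinic counselor for adherence counseling". Only the first alternative implies a recent HIV RNA.

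In section 6 (SAP), the secondary efficacy outcome is described so: "This will be assessed by comparing change in HIV viral load (from baseline to 24 weeks". The analysis is a "pre-post comparison of viral load measures at baseline and 24 weeks in the two study groups", using paired tests at the two-sided 5% level. The SAP has no rule for a missing baseline. It also plans exploratory univariate regressions, including a logistic regression of suppression at study end, but does not name study arm as a predictor.

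**The concern.** A paired test needs both values from the same person. A participant can attend every visit, provide a week-24 viral load and still contribute nothing, because the clinic happened not to test in the right window. This is separate from dropout: such a participant cannot be given a change score from the day of enrolment.

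Under the section 5 list the loss need not be random. A patient who qualifies through virologic failure in the preceding 3 months has a value in the window by definition, and it is a failing one. A patient who qualifies through MPR below 80% or referral may have none. If some have none, the paired sample leans towards people chosen for a recent high value, whose next value tends to be lower with or without the app. A within-group pre-post test has no control for that. The pilot is meant to be the basis for a larger trial (section 7), so an inflated change, or one from far fewer than 25 pairs per arm, could mislead its design.

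**Working it through.** **The plan's own figure.** Section 4: "participants will be randomized to receive the social incentive (n=25) or the social plus financial incentive (n=25"), so 25 + 25 = 50. The documents give no power, effect size or expected number of paired viral loads, so there is nothing further to reproduce.

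**Inputs not in the documents (assumed).** *T* = viral load testing interval in months, with tests spread evenly. *v* = share entering through virologic failure. The window is taken as the 3 months before enrolment. The chance that another entrant has a result in the window is then *q* = min(1, 3/*T*).

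**Step 1: section 4 list (no entry routes).** Pairs per arm = 25*q*; the standard error grows by √(1/*q*).
- 3-monthly testing: 25 pairs, no loss.
- 6-monthly: 12.5 pairs, SE × 1.41.
- Yearly: 6.25 pairs, SE × 2.0.

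**Step 2: section 5 list.** Share with a change score = *v* + (1−*v*)*q*. Failure entrants' share of the paired sample = *v* / [*v* + (1−*v*)*q*]. With *v* = 1/3:
- 6-monthly: 1/3 + 2/3 × 0.5 = 0.667, so 33% have no score, 16.7 pairs per arm, and failure entrants are 50% of the pairs.
- Yearly: 1/3 + 2/3 × 0.25 = 0.50, so 50% have no score, 12.5 pairs per arm, and failure entrants are 67% of the pairs.

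Across *v* = 0.2 to 0.6 and *q* = 0.75 to 0.25, total pairs run from 20 to 45 of 50. Failure entrants' share exceeds their enrolled share whenever *q* < 1 and equals it at *q* = 1.

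**Step 3: precision.** Detectable within-arm change for a paired t-test (two-sided 0.05; 80% power is my assumption): 0.58 SD at 25 pairs, 0.66 at 20, 0.78 at 15, 1.00 at 10.

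**Step 4: apparent rise in suppression with no app effect** (*v* = 1/3, failure entrants all viraemic at baseline). Two further inputs matter: suppression among the other entrants, and who can re-suppress. Section 2 reports that "40% of AYA who remained in care one year after starting ART had virologic failure (HIV RNA >1000 copies/mL"), which would give 60% suppressed. That is a general in-care group. Section 2 also gives 26% failure at MPR >94% and an adjusted risk ratio of 0.43 against MPR <80%; 0.26/0.43 ≈ 60% failure, or 40% suppressed (rough: an adjusted ratio, and two cited reports). The 40% re-suppression rate is assumed.

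| Assumption | Full cohort | Pairs, 6-monthly | Pairs, yearly | Excess (points) |
|---|---|---|---|---|
| A. Only failure entrants re-suppress | 0.4 × 1/3 = 13% | 0.133/0.667 = 20% | 0.133/0.50 = 27% | 7 to 13 |
| B. All viraemic patients can; others 60% suppressed | 0.4 × 0.60 = 24% | 0.4 × 0.70 = 28% | 0.4 × 0.80 = 32% | 4 to 8 |
| C. As B; others 40% suppressed | 0.4 × 0.733 = 29% | 0.4 × 0.80 = 32% | 0.4 × 0.867 = 35% | 3 to 5 |

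In B, for example, the viraemic share is 1/3 + 2/3 × 0.4 = 0.60 in the full cohort, and 0.5 + 0.5 × 0.4 = 0.70 in the 6-monthly pairs.

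**Step 5: overlap of routes.** Step 4 treats failure entrants as a separate group. If nobody qualifies through failure alone, and testing among the rest is unrelated to viral load, true baseline failure is the same in pairs and cohort (40% and 40%, taking 40% failure in that pool). If 20% qualify through failure alone and *q* = 0.5, it is (0.2 + 0.8 × 0.5 × 0.4)/(0.2 + 0.8 × 0.5) = 60% in the pairs, against 0.2 + 0.8 × 0.4 = 52% in the cohort.

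**The case against.** A baseline draw may be intended. The study outcomes paragraph of section 4 speaks of clinical measures taken at baseline and at each visit. Section 5, B.1 treats Aim 2 as research involving bodily samples. The consent forms and questionnaire are visible only as titles. A fallback draw therefore cannot be excluded from what can be read. But neither place names a baseline HIV RNA draw, and the one sentence that names a source names the clinic record.

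The window is not stated to be before enrolment. If results up to 3 months on either side count, nobody is lost at 6-monthly testing, although under the section 4 list half still are at yearly testing. This stands as a limit on the size.

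A reader might infer that the paired sample necessarily over-represents failure entrants. The documents do not support that. It needs the fifth criterion, which is absent from the section 4 list, and it needs some low-MPR or referral entrants without a result. A reader might also take row A of the table as the expected distortion. It lets failure entrants re-suppress but no other viraemic patient, which nothing in the documents justifies. Rows B and C show that the full cohort itself carries most of the no-effect rise, so the uncontrolled pre-post design is the larger weakness.

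The SAP's regression of suppression at study end needs no baseline, so *cannot be scored* applies to viral load change only. That regression is exploratory and does not name arm, so it does not fill the gap.

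Finally, this is one secondary outcome in a 50-person pilot whose primary outcomes are feasibility, acceptability and appropriateness scores. That limits the consequences; it does not remove the gap.

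**Conclusion.** The gap is real: paired viral load change depends on a record value that no eligibility rule secures, and the SAP does not say what happens without one. Under the section 4 list the clear cost is precision. Under the section 5 list, if some low-MPR or referral entrants lack a result, there is also selection towards recent failing values and so towards apparent improvement. The two lists must be reconciled before one can say which applies.

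The size cannot be fixed from the documents. With one third entering through failure and a window before enrolment, 33% to 50% would have no change score at 6-monthly to yearly testing. The excess no-effect rise would be roughly 3 to 13 points, with the top of that range resting on row A. It is zero if everyone has a result, and Step 5 shows that it can also vanish when no one qualifies through failure alone. The point is worth acting on because the remedy is cheap, not because a large bias has been shown.

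**What to change.** In section 6:

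1. Add a comparison of PEER with PEER+ on viral suppression at 24 weeks in all randomised participants with a week-24 result. Build it on the end-of-study suppression regression already planned, with arm as the predictor and baseline HIV RNA as a category that includes *no result in window*. Nobody is then dropped for want of a baseline.
2. Keep the within-group paired change, because both arms receive the app and the between-arm contrast cannot show the effect of the app itself. Label it as restricted to participants with a baseline value, and give its N by arm and by entry route.

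The cost is SAP wording, one more model and one table, with no new data. The paired result carries less weight. The between-arm estimate will be imprecise: at 50% suppression and 25 per arm its standard error is √(2 × 0.25/25) = 0.14, a 95% interval of about ±28 points, so it should be reported as an estimate with its interval.

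I would not add a recent HIV RNA result to the eligibility criteria. That could exclude poorly adherent patients who have not been tested recently.
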